### Commercially Confidential Information

Women of child bearing potential must be informed that taking the study treatment may involve unknown risks to the fetus if pregnancy were to occur during the study and must agree that in order to participate in the study they must adhere to the contraception requirements outlined in the exclusion criteria. If there is any question that the subject will not reliably comply, they should not be entered or continue in the study.

As of January 2018, over 2830 subjects have been exposed to fevipiprant in its clinical development program. Potential side effects of fevipiprant include: increased heart rate, non-serious arrhythmia such as palpitations, headache, diarrhea, nausea, vomiting, nasopharyngitis, somnolence and dizziness.

Cardiovascular risks will be monitored based on changes in vital signs, ECGs and biochemical parameters. Monitoring of liver function tests (LFT) and renal function will be conducted.

In humans, one major metabolite of fevipiprant has been identified which is formed by glucuronidation (acyl glucuronide) and partially binds to plasma proteins. In the literature, in vivo binding of acyl glucuronides to proteins has been reported to be associated with rare idiosyncratic drug reactions (IDRs), although a causal connection of protein adduction to IDRs remains uncertain. There have been no IDRs observed with fevipiprant treatment in completed clinical trials as of January 2018. Surveillance of adverse events for identification of IDRs will be conducted during the course of this study.

Taking fevipiprant at the doses used in this study with the cholesterol-lowering drug simvastatin has been shown to cause a small increase in the peak blood level of simvastatin. Subjects on doses of simvastatin > 20 mg, doses of atorvastatin > 40 mg, doses of pravastatin > 40 mg, or doses of pitavastatin > 2 mg per day, as well as subjects on any statins with high creatine kinase (CK) levels (> 2 X ULN (upper limit of normal)) at screening will be excluded from the study. Subjects on statin medication who are included in the study will have regular monitoring for relevant symptoms and be subject to discontinuation based on persistent myalgia and/or blood CK levels.

Kindly refer to the Investigator's Brochure for further guidance on the risk-benefit assessment of fevipiprant.

#### 4.5.1 Blood sample volume

A volume smaller than a typical blood donation is planned to be collected over a period of approximately 4 months from each subject as part of the study. Additional samples may be required for safety monitoring.

Timings of blood sample collection are outlined in the Assessment Schedule ([Table 8-1](#)).

A summary blood log is provided in the Site Operations Manual (SOM). Instructions for all sample collection, processing, storage and shipment information is available in the Central Laboratory Manual.

Commercially Confidential Information

### 5 Population

The study population will comprise of approximately 50 male or female patients with moderate to severe COPD on standard of care medications. They must demonstrate an eosinophilic phenotype as defined by a sputum eosinophil count of  $\geq 3\%$  of the total cell count obtained from an induced sputum specimen and documented evidence of a peripheral eosinophil count  $\geq 300$  cells/ $\mu\text{L}$  of blood at the screening visit, or within three months prior to the screening visit.

Subject selection is to be established by checking through all inclusion and exclusion criteria following completion of all screening/baseline assessments. A relevant record (e.g. checklist) of the eligibility criteria must be stored with the source documentation at the study site. No additional exclusions may be applied by the investigator, in order to ensure that the study population will be representative of all eligible subjects.

Deviation from **any** entry criterion excludes a subject from enrollment into the study.

Replacement subjects may be enrolled to replace subjects who discontinue the study for reasons other than safety.

Screening and Baseline safety laboratory tests can be repeated once, if deemed appropriate by the Investigator.

#### 5.1 Inclusion criteria

Subjects eligible for inclusion in this study must meet **all** of the following criteria:

1. Written informed consent must be obtained before any assessment is performed.
2. Able to communicate well with the investigator, to understand and comply with the requirements of the study.
3. Male and female adult patients aged  $\geq 40$  to  $\leq 80$  years at screening visit.
4. Acceptable and reproducible spirometry with post-bronchodilator FEV1/FVC  $< 0.7$  and post-bronchodilator FEV1  $\geq 30$  and  $\leq 80\%$  of predicted at the screening and baseline visits (GOLD stage II or III COPD). Note: re-testing is allowed once.
5. Patients with a physician-diagnosed history of COPD for at least 1 year prior to screening visit, and a documented history of at least one COPD exacerbation within the year prior to screening.

6. Patients on a stable therapy regimen for COPD for at least 4 weeks prior to screening visit with inhaled glucocorticoid + one or more long acting bronchodilator.
7. Documented elevated peripheral blood eosinophil count  $\geq$  300 cells/ $\mu$ L blood either at the Screening visit or at any time in the preceding 3 months. Sputum eosinophils must be  $\geq$  3% of total cell count at the baseline sputum collection. Note: re-testing for each is allowed once.
8. Current or ex-smokers who have a smoking history of at least 10 pack-years (10 pack-years are defined as 20 cigarettes a day for 10 years, or 10 cigarettes a day for 20 years, or equivalent).
9. Able to produce good quality induced sputum sample at the baseline sputum induction visit. Note: can be repeated once.

## 5.2 Exclusion criteria

Subjects meeting any of the following criteria are not eligible for inclusion in this study.

1. Patients with a past or current medical history of asthma.
2. History of hypersensitivity to any of the study treatments or study drug excipients (including milk or lactose) or to drugs of similar chemical classes.
3. Patients who have had a respiratory tract infection or COPD worsening or systemic steroid use within 4 weeks prior to screening visit or between the screening and randomization visits. Patients may be re-screened 4 weeks after recovery from their respiratory tract infection or COPD worsening or completion of steroid treatment.
4. Patients with a current or past medical history of conditions other than COPD or allergic rhinitis that could result in elevated sputum eosinophils (e.g., asthma, hypereosinophilic syndrome, Churg-Strauss Syndrome). Patients with known parasitic infestation within 6 months prior to screening are also excluded.
5. Patients with history of concomitant chronic or severe pulmonary disease (e.g., sarcoidosis, interstitial lung disease, cystic fibrosis, tuberculosis). Exception: Patients with concomitant mild or moderate pulmonary hypertension or bronchiectasis are permitted to participate.
6. Patients with a clinical diagnosis of  $\alpha$ -1 anti-trypsin deficiency (heterozygous genotype may be enrolled).
7. Pregnant or nursing (lactating) women.
8. Women of child-bearing potential, defined as all women physiologically capable of becoming pregnant, unless they are using basic methods of contraception during the study. Basic contraception methods include:
  - Total abstinence (when this is in line with the preferred and usual lifestyle of the subject). Periodic abstinence (e.g., calendar, ovulation, symptothermal, post-ovulation methods) and withdrawal are not acceptable methods of contraception.
  - Female sterilization (have had surgical bilateral oophorectomy with or without hysterectomy), total hysterectomy or tubal ligation at least six weeks before taking investigational drug. In case of oophorectomy alone, only when the reproductive status of the woman has been confirmed by follow up hormone level assessment.

- Male sterilization (at least 6 months prior to screening). For female subjects on the study, the vasectomized male partner should be the sole partner for that subject.
- Barrier methods of contraception: Condom or Occlusive cap (diaphragm or cervical/vault caps) if allowed as effective method of contraception by local regulations. For United Kingdom: with spermicidal foam/gel/film/cream/ vaginal suppository.
- Use of oral, (estrogen and progesterone), injected or implanted hormonal methods of contraception or other forms of hormonal contraception that have comparable efficacy (failure rate <1%), for example hormone vaginal ring or transdermal hormone contraception or placement of an intrauterine device (IUD) or intrauterine system (IUS).

In case of use of oral contraception women should have been stable on the same pill for a minimum of 3 months before taking investigational drug.

Women are considered post-menopausal and not of child bearing potential if they have had 12 months of natural (spontaneous) amenorrhea with an appropriate clinical profile (e.g. age appropriate, history of vasomotor symptoms) or have had surgical bilateral oophorectomy (with or without hysterectomy), total hysterectomy or tubal ligation at least six weeks ago. In the case of oophorectomy alone, only when the reproductive status of the woman has been confirmed by follow up hormone level assessment is she considered not of child bearing potential.

If local regulations deviate from the contraception methods listed above to prevent pregnancy, local regulations apply and will be described in the ICF.

9. Patients with any of the following cardiac related concerns:

- A resting QTcF (Fridericia)  $\geq 450$  msec (male) or  $\geq 460$  msec (female) at screening or baseline visit.
- A history of familial long QT syndrome or known family history of Torsades de Pointes.
- Receiving any medications or other agents known to prolong the QT interval.
- Patients with a history of moderate or severe uncontrolled tachyarrhythmias.
- History of a clinically significant cardiovascular event within 1 year prior to the screening visit, such as acute myocardial infarction, congestive heart failure, unstable arrhythmias.
- Patients who, in the judgment of the investigator have a clinically significant ECG abnormality such as (but not limited to) sustained ventricular tachycardia, or clinically significant second or third degree AV block without a pacemaker.

10. Patients on any statin therapy with a CK level  $> 2 \times$  ULN at screening or baseline visit.

11. Patients who have a clinically significant laboratory abnormality at the screening or baseline visit including (but not limited to):

- Total white blood cell count  $< 2500$  cells/uL;
- AST or ALT  $> 2.0 \times$  ULN or total bilirubin  $> 1.3 \times$  ULN;
- Estimated Glomerular Filtration Rate (eGFR) by the Modification of Diet in Renal Disease (MDRD) equation or Bedside Schwartz equation  $< 55$  mL/minute/1.73 m^2.

12. History of immunodeficiency diseases, or a positive HIV (ELISA and Western blot) test result at the screening visit.
13. Chronic infection with Hepatitis B (HBV) or Hepatitis C (HCV). A positive HBV surface antigen (HBsAg) test excludes a subject. Subjects with a positive HCV antibody test should have HCV RNA levels measured. Subjects with positive (detectable) HCV RNA should be excluded.
14. Patients who have a history of or current treatment for hepatic disease including but not limited to acute or chronic hepatitis, cirrhosis or hepatic failure.
15. Any severe, progressive or uncontrolled, acute or chronic, medical or psychiatric condition, or other factors such as abnormal vital signs, ECG or physical findings, or clinically relevant abnormal laboratory values, that in the judgment of the investigator may increase the risk associated with study participation/treatment or may interfere with interpretation of study results, and thus would make the patient inappropriate for entry into or continuing the study.
16. Donation or loss of 400 ml or more of blood within 8 weeks prior to screening, or longer if required by local regulation.
17. History of drug or alcohol abuse within the 12 months prior to dosing.
18. At screening, history or symptoms of malignancy of any organ system (except for a history of basal cell carcinoma and/or up to 3 squamous cell carcinomas of the skin, if successful treatment has been performed, with no signs of recurrence; actinic keratosis, if present at screening, should be treated according to standard therapy before randomization), treated or untreated, within the past 5 years, regardless of whether there is evidence of local recurrence or metastases.
19. Patients on prohibited treatment listed in [Table 6-2](#).
20. Use of other investigational drugs at the time of enrollment, or within 5 half-lives of experimental drug at the time of enrollment, or within 30 days of last dose of experimental drug at the time of enrollment, whichever is longer; or longer if required by local regulations.

## 6 Treatment

### 6.1 Study treatment

Details on the requirements for storage and management of study treatment, and instructions to be followed for subject numbering, prescribing/dispensing, and taking study treatment are outlined in the SOM.

### 6.1.1 Investigational and control drugs

**Table 6-1 Investigational and control drug**

Investigational/ Control Drug (Name and Strength)	Pharmaceutical Dosage Form	Route of Administration	Supply Type	Sponsor (global or local)
QAW039 450mg	Tablet	Oral use	Double Blind supply; bottle	Sponsor (global)
QAW039 Placebo	Tablet	Oral use	Double Blind supply; bottle	Sponsor (global)

### 6.1.2 Additional study treatments

Commercially Confidential Information

### 6.1.3 Treatment arms/group

Subjects will be assigned at or after visit 30 to one of the following two treatment arms/groups in a ratio of 3:2 active fevipiprant (QAW039) vs placebo.

## 6.2 Other treatment(s)

Oral contraception is permitted as a concomitant medication.

Prohibited medications are listed in [Table 6-2](#).

### 6.2.1 Concomitant therapy

Subjects should remain on their baseline regimen of inhaled corticosteroid (ICS) plus one or more long acting bronchodilator (long-acting beta2-agonist (LABA) or long-acting antimuscarinic antagonist (LAMA) from at least four weeks prior to the Screening visit through to the End of Study/Early Termination visit, with short-acting bronchodilators taken as rescue medication on an “as needed” basis for symptoms.

Other concomitant medications can continue during the study, provided they are not prohibited (see [Table 6-2](#)).

All medications, procedures, and significant non-drug therapies (including physical therapy and blood transfusions) administered after the subject was enrolled into the study must be recorded on the appropriate Case Report Forms.

Each concomitant drug must be individually assessed against all exclusion criteria/prohibited medication. If in doubt, the investigator should contact the Novartis medical monitor before randomizing a subject or allowing a new medication to be started. If the subject is already enrolled, contact Novartis to determine if the subject should continue participation in the study.

### 6.2.2 Prohibited medication

Use of the treatments displayed in the below table are not allowed for the time defined in the 'Prohibition period'.

**Table 6-2 Prohibited medication**

Medication	Prohibition period	Action taken
> 20 mg simvastatin > 40 mg atorvastatin > 40 mg pravastatin > 2 mg pitavastatin	From 4 weeks prior to screening visit and for the duration of study  (Rationale: Risk of over-exposure to concomitant medication due to OATP1B1 inhibition)	Exclude subject from study/Discontinue study treatment if initiated after randomization
Cyclosporin, rifampin, probenecid, ritonavir, valproic acid (i.e. medications blocking several pathways important for the elimination of QAW039 (broad range UGT inhibition and/or inhibition of OAT3, OATP1B3, MXR and Pgp))	From 4 weeks prior to screening visit and for the duration of study  (Rationale: Risk of over-exposure to QAW039)	Exclude subject from study/Discontinue study treatment if initiated after randomization
Any medication or other agents, such as Azithromycin, known to significantly prolong the QT interval	From 4 weeks prior to screening visit and for the duration of study  (Rationale: To avoid risk of QT prolongation)	Exclude subject from study/Discontinue study treatment if initiated after randomization
Systemic glucocorticoids	From 4 weeks prior to screening visit and for the duration of study  (Rationale: Confounds primary objective)	Exclude subject from study/Discontinue study treatment if initiated after randomization

Commercially Confidential Information

Comercially Confidential Information

### **6.2.3      Rescue medication**

Unless clinically indicated, the type of rescue medication      CCI      a subject uses, the device used to deliver the medication (e.g., dry powder or HFA) and the way it is administered (e.g., with a spacer device) should not be adjusted.      Comercially Confidential Information

### **6.2.4      Restriction for study subjects**

For the duration of the study, subjects should be informed and reminded of the restrictions outlined in this section.

#### **6.2.4.1    Dietary restrictions and smoking**

Study participants should refrain from alcohol, caffeine and smoking for at least 4 hours prior to study visits. The study drug can be taken with or without food.

#### **6.2.4.2    Other restrictions**

- For women of childbearing potential, the contraception requirements as outlined in the Exclusion Criteria in [Section 5.2](#)
- No strenuous physical exercise (e.g. weight training, aerobics, football) until after the End of Study/Early Termination visit.

## **6.3        Subject numbering, treatment assignment, randomization**

### **6.3.1      Subject numbering**

The subject number assigned to a subject at screening remains the unique identifier for the subject throughout the study. For information on subject numbering, please see 'Subject numbering' section in the Site Operations Manual.

### **6.3.2      Treatment assignment, randomization**

The randomization numbers will be generated using the following procedure to ensure that treatment assignment is unbiased and concealed from subjects and investigator staff. A subject randomization list will be produced by the Interactive Response Technology (IRT) provider using a validated system that automates the random assignment of subject numbers to randomization numbers. These randomization numbers are linked to the different treatment arms, which in turn are linked to medication numbers. A separate medication list will be produced by or under the responsibility of Novartis Global Clinical Supply (GCS) using a validated system that automates the random assignment of medication numbers to packs containing the study treatment.

Randomization will be stratified by current smoking status (current vs. ex smoker).

The randomization scheme for subjects will be reviewed and approved by a member of the Randomization Office.

## **6.4 Treatment blinding**

This is a subject and investigator-blinded study. Subjects, investigators and all site staff will remain blinded to study treatment throughout the study.

Unblinding a single subject at site for safety reasons (if necessary for subject management) will occur via an emergency system in place at the site.

The identity of the treatments will be concealed by the use of study drugs that are all identical in packaging, labeling, schedule of administration, appearance, and odor.

The sponsor may be unblinded to the study treatment at any time, especially in case of a safety concern.

The sample analysts will receive a copy of the randomization schedule (via request to the Randomization Office), to facilitate analysis of the samples.

The study statistician will be able to access the randomization list and is allowed to share unblinded information with the rest of the clinical team as appropriate for internal decision purposes. For example, unblinded summaries and unblinded individual data can be shared with the team for interim analyses.

Study programmers and other personnel involved in study data analysis ( CCI ) are allowed to access treatment assignment information for the purpose of conducting analyses.

The clinical trial team is allowed to share unblinded results with other sponsor staff (e.g. decision boards) as required for internal decision making on the study or the project while the study is ongoing.

The sponsor does not intend to share unblinded data with study site staff or with study subjects while the study is ongoing.

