## 8.3 Efficacy

Pharmacodynamic samples and measurements will be collected at the timepoints defined in the Assessment Schedule ([Table 8-1](#)). Follow instructions outlined in the Site Operations Manual and Central Laboratory Manual regarding sample collection, numbering, processing, and shipment and instructions.

Pharmacodynamic (PD) samples will be obtained and evaluated in all subjects at all dose levels, including the placebo group.

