### 8.3.1 Sputum eosinophil % of total cell count

Sputum will be induced with isotonic or hypertonic saline with appropriate safety measures as per the Sputum induction protocol.

If sputum induction is contraindicated at the planned visit, or if insufficient/inadequate/poor quality sputum sample is obtained upon induction, the procedure can be repeated/rescheduled within two weeks after the planned visit (a window of 3 days or more should occur between consecutive sputum induction assessments).

If a repeat/reschedule of the sputum induction is necessary at the End of Treatment visit, the subject should continue to take their study medication until the assessment is repeated (up to a total of eight weeks treatment duration).

Induced sputum will be processed at site for the following analysis: 1. preparation of cytospin slides for differential cellular count (primary endpoint); 2. remaining supernatant from cytospin preparation used for biomarker assessments; 3. RNA profiling of sputum cells (if sufficient sputum plug samples are available).

Full details on the sputum induction process are provided in the Sputum induction protocol.

Commercially Confidential Information

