#### **12.4.1 Definition of primary endpoint(s)**

The primary variable of the study is the change from baseline in sputum eosinophil percentage at week 6. As sputum eosinophil percentage has been found to follow a log-normal distribution, the analysis will be based on log10-transformed scale. The baseline measurement is defined as sputum eosinophil percentage prior to the first dosing (on log10-transformed scale).

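### Protocol 6.4 gives the randomization schedule to the sample analysts without limiting this to drug-concentration assays, and no visible text blinds the readers of the sputum slides behind the primary endpoint

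*Protocol*

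**What the plan says.** Section 6.4 of the protocol sets out who is blinded and who is not. On the blinded side: "Subjects, investigators and all site staff will remain blinded to study treatment throughout the study". On the unblinded side it lists several groups. For laboratory staff: "The sample analysts will receive a copy of the randomization schedule (via request to the Randomization Office), to facilitate analysis of the samples". For the statistician: "The study statistician will be able to access the randomization list". Programmers and other personnel who analyse study data "are allowed to access treatment assignment information for the purpose of conducting analyses".

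Section 12.4.1 defines the endpoint: "The primary variable of the study is the change from baseline in sputum eosinophil percentage at week 6". The percentage comes from a differential count on cytospin slides. Section 8.3.1 says: "Induced sputum will be processed at site for the following analysis", and lists slide preparation for that count first. It does not visibly say who counts the cells, or where.

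Section 8.3 says: "Pharmacodynamic (PD) samples will be obtained and evaluated in all subjects at all dose levels, including the placebo group". It refers to the Site Operations Manual and the Central Laboratory Manual for handling and shipping these samples.

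**The concern.** In a trial with a laboratory-read primary endpoint, the person who produces the reading should not know the arm. Here the plan blinds subjects and sites, but the only visible sentence on laboratory analysts gives them the schedule. It is worded as something that will happen, not as an exception, and it carries no limit by assay or laboratory.

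Statistician and programmer access is a different matter. Those staff work on values already recorded, whereas a slide reader creates the value. If the differential count involves judgement in classifying cells (an assumption, since the visible text does not describe the reading method), blinding at the site does not protect a count made elsewhere by someone who knows the arm. The protocol says in Sections 4.1 and 4.3 that blinding and placebo are there to limit bias and give an unbiased comparison, so an explicit rule for slide readers serves its own stated aim.

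**Working it through.** There is no plan figure to reproduce. The check sets the passages side by side and then counts the slides within reach.

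1. **Is the release limited to drug-concentration work?** Not in the words of 6.4. The term *samples* does not supply the limit either, because 8.3 uses it for pharmacodynamic material as well.

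2. **Is there a visible reason for pharmacodynamic analysts to hold the schedule?** No. Section 8.3 has these samples evaluated in every subject, placebo included, so the schedule is not needed to choose which samples to process. This suggests that the sentence was meant for drug-concentration assays, but it does not say so.

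3. **Are slide readers blinded by some other sentence?** That depends on where they work.
   - *Site staff read the slides:* the site-staff sentence in 6.4 covers them, and no gap remains.
   - *Off-site staff read the slides:* no visible sentence in either document covers them.

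4. **Do the documents settle the place of reading?** No. Section 8.3.1 places processing and slide preparation at the site and stops there. Section 8.3 refers to shipment instructions for pharmacodynamic samples. Table 8-1 marks induced sputum with a code that covers both entry in the clinical database and electronic receipt from a vendor. Off-site reading is therefore possible but not shown.

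5. **Which slides could be affected?**
   - *Baseline:* not exposed. Inclusion criterion 7 in Section 5.1 requires at least 3% eosinophils at baseline, so this count must be known before randomization.
   - *Week 6 (primary):* Section 12.8.1 plans about 30 fevipiprant and 20 placebo completers, and Section 12.4.3 uses one post-treatment sample each. 30 + 20 = 50, and 50 × 1 = about 50 samples.
   - *End of study:* Section 3 and Table 8-1 schedule a further induction about 4 weeks after the last dose. If every completer gives that sample (an assumption), this adds about 50, so 50 + 50 = about 100 post-baseline samples.

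These are planned numbers. SAP Section 2 records early termination, and the visible text does not give the number collected. The size of any bias cannot be derived from the documents, because it would require an assumed rate of misreading.

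**The case against.** The strongest reply is that the gap depends on text that cannot be seen. Harm needs three conditions together: slides read off-site, slide readers counted among the sample analysts, and no restriction elsewhere. None is established. The Site Operations Manual, Central Laboratory Manual and Sputum induction protocol were not supplied. Text near 8.3.1, 8.3.3 and 8.5.3 is redacted, as is the SAP table on derivations for sputum samples. What is hidden cannot be counted as absent. This stands, and it is why the point is conditional.

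A second reply is that the sentence states a purpose and routes access through a request to the Randomization Office, so a sensible reading excludes slide readers. That may be the intent. However, a purpose is not a limit, and the sentence itself is unredacted and unrestricted. If a manual does restrict access, 6.4 should be brought into line with it.

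A third reply is that the study has ended, so rewording cannot change slides already read. This also largely stands. What clearly still applies is a record of who held the schedule, since the SAP supports the study report and its Section 6.1.2 keeps the same primary variable.

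A reader might infer that the slides were in fact read unblinded, or that the primary result is biased. The documents support neither. They show a permission that may or may not extend to the readers, and nothing about what was done.

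**Conclusion.** The point holds in conditional form. Section 6.4 releases the schedule to sample analysts without limiting it to drug-concentration assays, and no visible text blinds the readers of the slides that give the primary endpoint. If reading is at the site, the readers are already blinded. If it is off-site, the wording permits reading with the arm known for about 50 planned week-6 slides, and for the end-of-study slides as well.

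This rests on two assumptions: that the count depends in part on the reader's judgement, and that no restriction sits in the manuals or the redacted text. No amount of bias is claimed. This is a cheap improvement, not a demonstrated flaw in the primary result.

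**What to change.** In Section 6.4, limit release of the schedule to analysts measuring drug concentration, plus any other assay the sponsor names as needing it. The second part matters because the pharmacokinetic and biomarker text is redacted, so a blanket rule for all other analysts cannot be judged from here.

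State in Sections 6.4 and 8.3.1 that readers of sputum cytospin slides stay blinded to treatment until their counts are final, wherever the reading takes place. Leave statistician and programmer access as it is.

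Because the study ended early, record in the study report who received the schedule and whether the slide readers were blinded. Requests already pass through the Randomization Office, so the record should be short.

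The cost is a small written amendment with the approvals that Section 14.1 requires (sponsor, ethics committee, and health authorities where applicable), plus the access record. Study procedures, sample size and analysis do not change.
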